Service Dog Training Program for Military Veterans With PTSD

NCT03777020

05-30-2023

Protocol

This RCT will gather data from 60 veterans with Post-traumatic stress disorder (PTSD) and 30 service dogs (SDs) in training. Veterans will be recruited and screened for eligibility according to Warrior Canine Connection (WCC) inclusion criteria Humans: 1) military veteran; 2) diagnosis of PTSD; 3) able to give informed consent; and 4) able to understand English. Human Exclusion Criteria: 1) fear of dogs; 2) allergy to pet dander; 3) active substance abuse; 4) active psychosis, or 5) history of animal abuse. Dog Inclusion Criteria: 1) non-aggressive demeanor as evaluated by WCC protocols for evaluating animal temperament; 2) cleared by veterinarian; and 3) up-to date immunizations. Dog Exclusion Criteria: 1) medical holds.

Recruitment/Screening: Recruitment will be via media attention, flyers, social media, and word of mouth.

Procedures: Veterans interested in the participating in the study will be prescreened by a research team member(RTM) for eligibility. Eligible veterans will be invited to participate. If veterans agree to participate after their questions are answered. They will be consented verbally, randomized, and scheduled for their first session with the location dependent on the arm. After informed consent is signed, baseline data will be obtained in an outdoor area at WCC [service dog training program(SDTP) arm] or at another meeting place near the participant's home [wait list control intervention((WLCI) arm)].

Randomization: Participants will be block randomized, according to gender, into the SDTP or WLCI. Group assignments will be generated by a computerized random number table and envelopes will be opened after verbal informed consent. Participants will continue existing therapies and begin any for which they are referred while in the study.

Interventions:

SDTP-Intervention (human): Veterans randomized to the SDTP will be paired with an experienced WCC Mission Based Trauma Recovery (MBTR)-Trainer (MBRT-T) and a SD. One hour training modules will be scheduled once a week for 8 weeks. Participants will come to WCC for all the weekly training modules. The MBTR-T will deliver the prescribed SDTP modules created by WCC. Each session will be fully supervised by a WCC MBTR-T to address any concerns or safety issues that may arise.

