b) Psychosocial health related to PTSD will be assessed with well validated scales, including PROMIS measures: Positive Affect-Short Form 15 (PA 15a),⁷⁵ PROMIS Satisfaction with Social Roles and Activities (SSRA) – Short Form 4a (PROMIS-SSRA),^{80,81} PROMIS Short Form v1.0- Satisfaction with Participation in Discretionary Social Activities- Short Form 7a (PROMIS SPDSA),^{82,83} PROMIS Companionship – Short Form 4a (PROMIS-C),^{84,85} PROMIS Depression Short-Form 8a,⁸⁷ and the PROMIS Anxiety Short-Form 8a.⁸⁸ Suicide ideation (SI) will be assessed with the Beck Scale for Suicide Ideation.⁸⁹ Quality of life will be assessed with the Veterans RAND 12-Item Healthy Survey,⁷⁶ Resilience will be assessed with the Connor-Davidson Resilience Scale (CD-RISC-10),⁷⁸ and Quality of an individual's relationships will be assessed with the Relationship Scale Questionnaire (RSQ).⁷⁹

c) The exploratory outcome: cellular aging will be assessed by obtaining absolute telomere length analysis.⁹⁰

Aim 2 Outcome Assessment: Dog HRV, is a reliable measure of stress levels.^{59,91} will be measured with the PetPace Collar (<http://petpace.com>). This non-invasive, monitor wirelessly tracks the dog's HRV and a range of physical and behavioral parameters.

Aim 3 Outcome Assessment: Participant attendance and participation in each session will be recorded by the SD trainers. The SD trainers also keep extensive notes on the interactions between the veterans and the dogs. Documentation of unintended consequences such as aggressive behavior (on either part), allergic reactions, fearful behavior (on either part). These logs will be used to assess participation in the SDTP. Exit phone interviews will be used to obtain veterans' perceptions of the SDTP and their outcomes.

Data Analysis Plan

Human Data: Before analyses, data will be cleaned and illustrated graphically. Summary statistics will be calculated, assumptions examined, and transformations applied as needed. Demographics and baseline characteristics (e.g., PTSDSS, gender) will be compared between the SDTP and WLCI groups, and the relevant variables considered as covariates for multivariable longitudinal analyses. SPSS 25 will be used for all analyses. Significance for rejecting the null is set at $p \leq .05$, Bonferroni sequential corrections will be used for multiple comparisons. The intent-to-treat approach will guide hypothesis testing. Separate sets of analyses are conducted for each outcome.

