H1: Participants in the SDTP ($n = 30$) will demonstrate significantly greater improvement in outcomes from week 1 to weeks 4 and 8 than the WLCI ($n = 30$) in: a) PTSD symptom severity; b) stress markers (decreased cortisol, α -amylase, perceived stress; increased IgA, HRV); c) psychosocial health (increased positive affect, QOL, resilience, and relationships with friends and family, satisfaction with social activities and roles, companionship and decreased depression, anxiety, and suicide ideation); and d) exploratory stress marker cellular aging [increased TL, from weeks 1 to 8 only].

Linear mixed models (LMMs) with random intercepts (participant as a random variable) will be used to assess differences in changes in each outcome between the SDTP and WLCI participants, accounting for the correlation with the repeated measurements of each participant, and using all available data. Fixed effects will include group (SDTP or WLCI), week (1, 4 and 8), and their interaction, as well as the relevant covariates. The hypothesized effect of the intervention will be tested with the week by group interaction. Interactions of covariates (e.g. gender and age) with the group and time will be explored to provide information about their influence and for preliminary data to justify formal evaluation (with adequate power) in future studies. The multi-modal assessment in this study will provide the opportunity to explore characteristics that predict benefits.

Dog data: For analyses of data from dogs, demographics and baseline characteristics (e.g., size, gender, age), will be computed. The distributional characteristics of HRV (e.g., normality, outliers and missing) will be explored. Appropriate steps will be used as needed to ensure that applicable assumptions are met. Descriptive statistics will be computed for HRV by week and period (pre, during, and post).

H2: Dogs who participate in the SDTP will not experience increases in stress (decreases in HRV) from the 30 minutes before, to during, and after SDTP sessions. LMMs with random intercepts (dog as a random variable)

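### Trainers log dog fear and aggression, but only to assess participation; H2 and H3 judge dog stress by mean HRV alone, so a small distressed minority is easily missed and need not be reported beside them

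*Combined protocol and SAP*

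**What the plan says.** Under Aim 3 Outcome Assessment, the trainers keep notes on veteran-dog interactions and document unintended consequences, including "aggressive behavior (on either part), allergic reactions, fearful behavior (on either part". The next sentence gives the use of these records: "These logs will be used to assess participation in the SDTP".

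Under Aim 2 Outcome Assessment, the dog outcome is HRV from a collar. The collar has wider capability, "This non-invasive, monitor wirelessly tracks the dog's HRV and a range of physical and behavioral parameters", but no behavioural parameter is named in any analysis.

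In the Data Analysis Plan, H2 reads "Dogs who participate in the SDTP will not experience increases in stress (decreases in HRV" and covers the periods before, during and after sessions. H3 makes the same claim over the 8 weeks. Both are tested in one linear mixed model with a random intercept for dog: H2 by the contribution of period, H3 by the contribution of week (1, 4, 8).

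Three other places bear on the point, and the last two do not name dogs:

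- Dog data: the distribution of HRV, including outliers and missing values, will be explored.
- Feasibility data: dropout and adverse events will be described.
- Missing Data: a sensitivity analysis such as a pattern-mixture model follows if attrition is excessive or differs across groups, or if missingness is informative.

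**The concern.** H2 and H3 are claims of no harm. A method that overlooks a harmed minority errs toward the favourable answer. The period and week effects are averages over dogs, and a random intercept lets dogs differ in level but not in their response to sessions or weeks. No dog-level criterion is given.

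The trainers' records are direct observations of fear and aggression in individual dogs, yet nothing connects them to H2 or H3. The plan could be followed to the letter, report that dogs showed no increase in stress, and leave logged distress in a participation summary.

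Dogs that stop contributing raise a related problem. The entry criteria include "Dog Exclusion Criteria: 1) medical holds", but no text says how a dog that stops during the study is recorded or analysed. If a dog stops because it is not coping, its later HRV cannot enter the week effect.

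**Working it through.** The documents give no power calculation, margin, SD, HRV metric or within-dog correlation for the dogs, so there is no planned figure to reproduce. What follows is an illustration.

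**Inputs from the protocol**
- 30 dogs: "60 veterans with Post-traumatic stress disorder (PTSD) and 30 service dogs (SDs) in training".
- 3 periods and 3 weeks per dog (H2 model).
- Alpha: "Significance for rejecting the null is set at $p \leq .05". This stands under Human Data; I take it to apply to the dog model too.

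**Assumed inputs**
- Residual (within-dog) SD s, complete data, additive period and week effects.
- k of 30 dogs fall by D at week 8 only; the others do not change.

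**Step 1: shift in the mean.** m = (k/30) × D.
- k = 3, D = 1.5 s: m = 0.15 s.
- k = 3, D = 2 s: m = 0.20 s.

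**Step 2: power of the 2-df week test.** Each week has 30 × 3 = 90 values. With week means 0, 0 and −m, the squared deviations from their mean sum to (2/3)m². Noncentrality is therefore 90 × (2/3) × m²/s². Residual df = 270 − 30 − 2 − 2 = 236, and the 5% critical value of F(2, 236) is 3.03.

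| Dogs affected | Fall at week 8 | m | Noncentrality | Power |
|---|---|---|---|---|
| 3 of 30 | 1.5 s | 0.15 s | 1.35 | 16% |
| 3 of 30 | 2 s | 0.20 s | 2.40 | 26% |
| 5 of 30 | 1.5 s | 0.25 s | 3.75 | 39% |
| 9 of 30 | 1.5 s | 0.45 s | 12.15 | 88% |

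The formula ignores the extra scatter caused by dogs responding differently. Direct simulation gives slightly lower values: about 15%, 23%, 34% and 86%.

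**Step 3: a different scaling.** Let the fall be 1 *total* SD at week 8, with within-dog correlation 0.3, 0.5 or 0.7. Simulated rejection rates are then:
- 3 of 30 dogs: 11%, 13%, 19%.
- 6 of 30 dogs: 32%, 43%, 66%.
- 9 of 30 dogs: 65%, 79%, 96%.

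Figures for the H2 period test, with the fall in the during-session period, are nearly the same.

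**Step 4: dogs that leave.** If the 3 affected dogs leave before week 8, their week-8 fall is never observed. Simulated rejection is then 4% to 5%, the false-positive rate. Values from their earlier weeks remain in the model, so any earlier fall still counts.

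**Step 5: what a count would show.**
- If 10% of dogs are truly affected, the chance of at least one affected dog among 30 is 1 − 0.9^30 = 95.8%.
- With 0 of 30 dogs affected, the exact one-sided 95% upper bound is 1 − 0.05^(1/30) = 9.5%; the two-sided 95% interval is 0 to 11.6%.
- With 3 of 30, the exact two-sided 95% interval is 2.1% to 26.5%.

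**The case against.** A reader might infer that distressed dogs would not show at all. The documents do not support that. Adverse events and dropout are to be summarised, HRV outliers and missing values are to be explored under Dog data, and the Missing Data section can be triggered by informative missingness, which needs no second arm. Affected dogs could surface by any of these routes. What remains is that the feasibility and missing-data texts do not name dogs, that outliers are explored with a view to model assumptions, and that none of these results has to stand beside H2 and H3.

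A reader might also take the logs to be the only behavioural evidence. They are not, since the collar tracks behavioural parameters, although no analysis uses them.

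HRV is a deliberate choice, which the protocol calls reliable and supports with citations. That is a fair defence of HRV as the measure. It does not answer the point about averaging over dogs. The HRV-only criterion comes from the wording of H2 and H3, not from where the logs are assigned.

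In-session behaviour counts have no pre-session or control comparator, so they cannot by themselves show an *increase* in stress. This stands, and it is why the counts should accompany H2 and H3 rather than decide them.

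Finally, the documents describe no dog being withdrawn, and medical holds are an entry criterion. The part about leaving dogs is therefore a contingency the plan should cover, not a known event.

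**Conclusion.** The point holds in a limited form. The plan collects dog-level evidence of distress, states only a participation use for it, and draws its dog-welfare conclusion from mean HRV. A small affected minority could easily be missed by H2 and H3: with 3 of 30 dogs falling by 1.5 to 2 s at week 8 only, the week test rejects about 16% to 26% of the time. That minority need not be reported beside the conclusion.

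Low power for a small minority is not blindness to any minority. With 9 of 30 dogs affected, detection is 65% or more in the scenarios shown. All power figures rest on assumed SD, correlation and size of fall. The structural finding, that neither the logs nor departures of dogs are linked to H2 and H3, comes from the text and needs no assumption.

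**What to change.** - Use the existing trainer logs in Aim 2 as well as for participation. For each week, report the number of dogs and of sessions with fearful or aggressive behaviour by the dog.
- In the same table, give the number of dogs no longer contributing HRV, with the reason. Show numbers of dogs out of 30 with exact confidence intervals, and place the table beside the H2 and H3 results.
- Word the H2 and H3 conclusions as statements about mean HRV, and report any logged dog distress with them. I would not make the conclusion conditional on HRV and counts agreeing, because no threshold or comparator exists for such a rule.
- State that the informative-missingness sensitivity analysis also applies to dog HRV in H3.

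**Cost:** coding of notes already kept and one table. Why a dog stopped is not among the listed log items, so recording it is a small addition. The conclusion on dog stress may come out less favourable.

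### The random-intercept-only model imposes equal correlations across weeks 1, 4 and 8; if correlation falls with time, week-specific contrasts get wrong standard errors, while the named interaction test is only mildly affected

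*Combined protocol and SAP*

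**What the plan says.** The H1 paragraph of the Data Analysis Plan reads: "Linear mixed models (LMMs) with random intercepts (participant as a random variable) will be used to assess differences in changes in each outcome". The stated aim is "accounting for the correlation with the repeated measurements of each participant, and using all available data". On the mean model it says: "Fixed effects will include group (SDTP or WLCI), week (1, 4 and 8), and their interaction, as well as the relevant covariates". On the test: "The hypothesized effect of the intervention will be tested with the week by group interaction". H1 itself predicts "greater improvement in outcomes from week 1 to weeks 4 and 8".

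No random slope, residual covariance structure, robust standard error or degrees-of-freedom method is named. The Human Data paragraph promises a general check of assumptions, transformations where needed, a .05 significance level and sequential Bonferroni correction, but it does not define the family of comparisons. It names no covariance check and no fallback structure. Under Outcome Assessment, telomere length is measured at weeks 1 and 8 only; the other outcomes have three visits. The documents give no correlations or standard deviations over time.

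**The concern.** A random intercept with independent residuals is compound symmetry: a single within-person variance is averaged over the three visit pairs and then used for every contrast. Weeks 1 and 8 are the furthest apart, so their correlation may well be the lowest. If so, the averaged variance understates the uncertainty of the week 1-to-8 change and overstates that of the week 1-to-4 change.

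This matters because the 2-df interaction cannot say whether week 4, week 8 or both differ. Supporting H1 as written needs week-specific contrasts and intervals from this model. A transformation of the outcome is not a remedy for a correlation that falls with time.

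**Working it through.** **Inputs.** From the documents: 30 per arm, visits at weeks 1, 4 and 8, random intercept, alpha .05. Assumed: two-sided testing, independent residuals, week as a factor, complete data, and the correlations below. The plan has no power or error-rate figure to reproduce other than the nominal .05.

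**Formula.** Let n be the number per arm and s² the pooled within-person mean square.

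- Model variance of the group difference in change from week 1 to any later visit: 2·s²·(2/n).
- True variance for week 8: (V11 + V33 − 2·V13)·(2/n).
- With equal variances, true/model ratio for week 8: R = (1 − ρ18)/(1 − mean ρ). For week 4, ρ14 replaces ρ18.
- Approximate type I error: 2·[1 − Φ(1.96/√R)].

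**Example, .7/.7/.5** (weeks 1-4/4-8/1-8). Mean ρ = 1.9/3 = .633, so R = .5/.367 = 1.364. The model standard error is 1/√1.364 = .856 of the true one. Type I error is 2·[1 − Φ(1.96/1.168)] = 9.3%. For week 4, R = .3/.367 = .818, so that standard error is too large.

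**Calibration.** In 100,000 simulated trials per pattern under true compound symmetry (correlation .5 and .7), the week-8 contrast rejects in 4.9-5.1% and the 2-df interaction in 5.0%.

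**Results** (type I error in %; the last four columns are simulated, 100,000 trials per row):

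| ρ 1-4/4-8/1-8 | R, week 8 | model SE / true SE | formula, week 8 | week 8 | week 4 | 2-df interaction | linear-week slope |
|---|---|---|---|---|---|---|---|
| .75/.70/.65 | .35/.300 = 1.167 | .926 | 7.0 | 6.8 | 3.3 | 5.0 | 7.0 |
| .7/.7/.6 | .40/.333 = 1.200 | .913 | 7.4 | 7.3 | 3.9 | 5.1 | 7.2 |
| .7/.7/.5 | .50/.367 = 1.364 | .856 | 9.3 | 9.3 | 3.0 | 5.5 | 9.2 |
| .8/.8/.5 | .50/.300 = 1.667 | .775 | 12.9 | 13.0 | 1.7 | 6.8 | 12.9 |
| .8/.8/.4 | .60/.333 = 1.800 | .745 | 14.4 | 14.4 | 1.2 | 7.3 | 14.3 |

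**Other patterns, week-8 contrast.** Weekly first-order autoregression of .80 to .98 gives 8.2-10.7%. Random slopes (slope variance .005 to .04, week-1 intraclass correlation .6) give 6.6-11.5%. A rising SD (1, 1.1, 1.25) with constant correlation .6 gives only 5.3%, so growing spread of that size is not by itself the problem.

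**Dropout.** With 7% missing at week 4 and 15% at week 8 (assumed) and .7/.7/.5, 2,000 REML random-intercept fits give 8.2% for week 8 (Monte Carlo SE 0.6 points) and 4.9% for the interaction.

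**Unstructured covariance.** The week-8 type I error is 4.9-5.1% in every pattern tried. If compound symmetry is true, power for the week-8 contrast falls from 73.8% (116 df) to 73.1% (58 df) at noncentrality 2.62.

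**The case against.** A reader might infer that the trial's hypothesis test runs at 9-13% type I error. The documents do not support that. The test they name is the week-by-group interaction, week is listed as three visits, and no week-8 contrast is specified. As a 2-df test the interaction is inflated by about 0-2 points. If a significant interaction is required first, a false week-8 claim occurs in about 3.5% (.75/.70/.65) to 6.8% (.8/.8/.5) of trials. If the sequential Bonferroni family were the two follow-up contrasts (the plan does not say), the chance of any false claim would be 5.0-8.3% over the same range. This part of the objection stands.

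Three other strong readings also fail:

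- **All intervals are too optimistic.** Under falling correlation the week-4 contrast errs the other way, and telomere length has a single visit pair, so nothing is averaged over pairs.
- **The effect estimates are biased.** With complete data, categorical week and no covariates, the week-8 estimate is the difference in mean change under either covariance; only its standard error differs. The Feasibility data paragraph does not say how effect sizes are standardised, so nothing firm can be said about them.
- **Correlation is known to fall.** The documents give no evidence on this for any outcome.

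What the objection does not remove is that the plan names only one covariance component and no fallback, and that H1 needs week-specific statements.

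**Conclusion.** The point holds in limited form. It rests on independent residuals and on correlation that falls with time, neither of which the documents state. Under mild to steep falls, a nominal 95% interval for the week-8 group difference covers about 93% (100 − 6.8) to 87% (100 − 13.0), while the week-4 interval is too wide. The named test is close to nominal if week is a factor. If week were fitted as linear, which the plan does not state but does not expressly rule out, the named test would behave like the week-8 contrast. The plan should therefore be tightened, but its main test is not invalid as written.

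**What to change.** For the three-visit veteran outcomes:

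1. Replace the random intercept by an unstructured residual covariance over weeks 1, 4 and 8, with week as a factor and Satterthwaite degrees of freedom.
2. State whether the conclusion for each outcome rests on the 2-df interaction or on the week-8 contrast.
3. Pre-state a simpler structure for non-convergence that allows for the unequal 3- and 4-week gaps. A first-order autoregressive structure indexed by visit order would treat the gaps as equal.

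Telomere length needs no change on this account.

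The cost is a few sentences in the plan, six covariance parameters instead of two, and under 1 point of power for the week-8 contrast (73.8% to 73.1%) if compound symmetry is true.

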Waitlist Control Intervention (WLCI): Veterans randomized to WLCI will participate in one hour online SD training modules (<https://e-trainingfordogs.com>) scheduled once a week for 8 weeks but not interact with service dogs. The online training modules are delivered by experienced SD trainers and will employ parallel content to the WCC SDTP. Participants will participate from their homes or at a location of their choice in online training modules.

Outcome Assessment: In both groups, human's biological [e.g. salivary and heart rate variability (HRV)] markers except telomere length (TL) will be assessed in weeks 1, 4, and 8. TL will be assessed at weeks 1 and 8. Scales for and psychosocial data will be completed prior to session 1 and after sessions 4 and 8. HRV will be recorded in the human participants during SDTP sessions and for 30 minutes after sessions.

Assessment: Human Demographics and Characteristics Questionnaire will collect demographic/descriptive data on the human participants, such as gender, age, race, ethnicity, marital status, educational level, living arrangements, military history and pet ownership history. The order of the questionnaires will be randomized to minimize order effects. A dog demographics and characteristics questionnaire will collect demographic/descriptive data including dog's name, WCC dog trainer's name, gender, age, breed, and weight. Additionally, a photo will be taken to illustrate size and face.

Aim 1 Outcome Assessment:

Primary outcome: PTSDSS will be assessed with the PTSD Checklist for DSM-5 (PCL-5), a 20-item scale.^{70,71}

Secondary outcomes:

a) Stress markers will be assessed with salivary cortisol, α - amylase, and HRV, and the perceived stress scale. Heart rate variability (HRV) of veterans will be measured with a Polar H7 heart rate sensor worn around the chest and matching Polar V800 GPS Sports Watch worn around a wrist to save data from the heart rate sensor and download it for analysis. Perceived stress (PS) will be assessed with the Patient-Reported Outcomes Measurement Information System (PROMIS) Perceived Stress Fixed Form v2.0 (PROMIS, PS).^{72,73} and

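### H1 compares unadjusted changes from week 1; using the week-1 score as an adjuster, by either of two routes, would give a more precise test at little cost

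*Combined protocol and SAP*

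**What the plan says.** The H1 part of the Data Analysis Plan specifies the model: "Linear mixed models (LMMs) with random intercepts (participant as a random variable) will be used", "accounting for the correlation with the repeated measurements of each participant, and using all available data". On the mean structure it says "Fixed effects will include group (SDTP or WLCI), week (1, 4 and 8), and their interaction, as well as the relevant covariates". On the test it says "The hypothesized effect of the intervention will be tested with the week by group interaction". Week 1 is thus one of three response occasions, and the group main effect lets the arms differ there.

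The Human Data paragraph adds "Demographics and baseline characteristics (e.g., PTSDSS, gender) will be compared between the SDTP and WLCI groups, and the relevant variables considered as covariates". It does not say how a baseline score would enter a model in which that same score is already a response. Covariate interactions are exploratory only: "Interactions of covariates (e.g. gender and age) with the group and time will be explored". On model checking the text is "Summary statistics will be calculated, assumptions examined, and transformations applied as needed", and no alternative covariance is named.

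On timing, Outcome Assessment states "Scales for and psychosocial data will be completed prior to session 1 and after sessions 4 and 8". Under Procedures, randomization precedes the baseline measurement, and the place of that measurement depends on the arm. The Missing Data paragraph expects some missing values but gives no rate. No correlation, SD, effect size or power target appears anywhere.

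**The concern.** A difference in change subtracts the whole week-1 value. Unless the correlation between week 1 and week 8 is close to 1, this adds week-1 noise to the comparison. Adjustment subtracts only the part of the week-1 value that predicts the later score. With 60 participants and a PCL-5 score collected before session 1, the plan gives up precision that costs nothing to recover.

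There are two secondary cautions. Because baseline PTSD severity is listed as a candidate covariate, the team could add it as a main effect and believe that the test had been adjusted. Also, a random intercept imposes one correlation on all pairs of weeks. A week-8 effect reported from that model would look too precise if the correlation falls as visits lie further apart.

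**Working it through.** **Inputs.** From the documents: 30 per arm, weeks 1, 4 and 8, significance level 0.05. Assumed, because the documents give none: SD 1, rho 0.5 to 0.9, two-sided testing, effects of 0.3 SD at week 4 and 0.6 SD at week 8, and either complete data or random dropout of 10% after week 1 and 10% after week 4. No multiplicity correction is applied. The plan states no power figure to reproduce.

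**1. Variance of the week-8 contrast, complete data, equal correlation.**
- Planned: 2(1 - rho) × 2/n
- Adjusted: (1 - rho²) × 2/n
- Ratio: (1 - rho²) / [2(1 - rho)] = (1 + rho)/2, a cut of (1 - rho)/2

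At rho 0.5 and n = 30, the planned variance is 2 × 0.5 × 2/30 = 0.0667 (SE 0.258). The adjusted variance is 0.75 × 2/30 = 0.0500 (SE 0.224).

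| rho | planned SE | adjusted SE | variance cut |
|---|---|---|---|
| 0.5 | 0.258 | 0.224 | 25% |
| 0.7 | 0.200 | 0.184 | 15% |
| 0.8 | 0.163 | 0.155 | 10% |
| 0.9 | 0.115 | 0.112 | 5% |

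With the covariance estimated (40,000 simulated trials per value of rho), the model for weeks 4 and 8 gave cuts of 24.4, 13.6, 8.1 and 3.4%.

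**2. Two routes to the same gain.** Generalized least squares with known covariance gives the following ratios to the planned variance, in order of rho.
- Complete data: 0.750, 0.850, 0.900, 0.950 when week 1 stays a response with one common mean. These equal the covariate route.
- With dropout: 0.787, 0.874, 0.917, 0.959 for the common-mean model, and 0.803, 0.892, 0.935, 0.978 for weeks 4 and 8 with the week-1 score as covariate.

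**3. Power of the joint test over both weeks, planned against the covariate route.**
- Complete data: 53 vs 65%, 76 vs 81%, 91 vs 93%, 99.8 vs 99.8%.
- With dropout: 45 vs 54%, 67 vs 71%, 85 vs 87%, 99 vs 99%.

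**4. Week-1 score as a main effect only, week 1 still a response.** With complete data the interaction estimate is identical to the planned one (largest difference below 1e-14). With 20% dropout at rho 0.5, the true SE is 0.291 against 0.289 without the covariate, while the average reported SE falls from 0.278 to 0.268. Across the four values of rho, under the 10% + 10% dropout, type I error of the joint test is 5.8 to 6.6%, against 4.4 to 5.3% without the covariate.

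**5. Unequal correlations.** A random intercept in effect uses the average correlation, so the large-sample critical value for the week-8 contrast shrinks to 1.96 × √[(1 - average)/(1 - r18)], where r18 is the correlation of weeks 1 and 8. For 0.70/0.50/0.70 (weeks 1-4, 1-8, 4-8) the average is 0.633, giving 1.96 × √(0.367/0.50) = 1.68 and a type I error of about 9.3%. Simulation with complete data gives:

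| Correlations 1-4 / 1-8 / 4-8 | week-8 contrast, type I error | planned joint test, type I error | power: planned / unstructured change / adjusted |
|---|---|---|---|
| 0.70 / 0.65 / 0.70 | 6.2% | 5.0% | 72 / 68 / 76% |
| 0.70 / 0.60 / 0.70 | 7.3% | 5.1% | 68 / 61 / 71% |
| 0.75 / 0.60 / 0.75 | 8.8% | 5.4% | 71 / 61 / 71% |
| 0.70 / 0.50 / 0.70 | 9.2% | 5.5% | 62 / 51 / 64% |
| 0.80 / 0.50 / 0.80 | 13.0% | 6.8% | 67 / 51 / 64% |

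**6. If knowing the arm shifts week-1 answers by 0.2 SD.** A shift that persists to week 8 biases the adjusted effect by 0.2(1 - rho), that is 0.10, 0.06 and 0.04 SD at rho 0.5, 0.7 and 0.8. The change score has no bias. A shift that vanishes biases the change score by 0.20 SD and the adjusted effect by 0.2 × rho, that is 0.10, 0.14 and 0.16 SD.

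**The case against.** The strongest reply is that nothing here is wrong. H1 is worded as improvement from week 1, and the interaction tests exactly that. No power target is stated, so none is missed, and the gain depends on a correlation that the documents do not give. At rho 0.7 to 0.8 it is worth 2 to 5 points of power. All of this stands, and it is why the point is an improvement only.

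The reply is also right on the two cautions. The Human Data paragraph says only that relevant variables are considered; it does not commit to a baseline main effect in the PCL-5 model. The inflated error rates in step 5 belong to a single week-8 contrast, which H1 does not name as its test. The planned joint test stays at 5.0 to 5.5% in four of the five patterns and reaches 6.8% in the most extreme.

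Adjustment is also not uniformly safer. Baseline follows allocation, and step 6 shows that either analysis can be the more biased one, depending on whether a shift lasts.

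A reader might infer that precision improves only if week 1 is taken out of the response. Step 2 shows otherwise: a common week-1 mean gives the same gain with complete data and slightly more with dropout.

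**Conclusion.** The planned H1 test is valid under its own covariance but less precise than it could be. With 30 per arm and equal correlations, using week 1 as an adjuster lowers the week-8 variance by 25, 15, 10 and 5% at assumed rho 0.5, 0.7, 0.8 and 0.9. With 10% + 10% dropout the cuts are about 21, 13, 8 and 4% by the common-mean route. The gain is small at high rho. Under strong decay of correlation there may be no raw power gain over the planned test, although adjustment gains 8 to 13 points over the change model with an unstructured covariance, which holds 5%.

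The documents do not support reading this as an invalid primary test or an underpowered trial. They fix neither the correlation nor a power target, and under equal correlation the planned test holds its 5% level. Both adjusted routes assume that week-1 values are unaffected by arm.

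**What to change.** For PCL-5 and the other scales completed before session 1, choose one route in advance:

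- **(a)** Weeks 4 and 8 as responses, with group, week, group-by-week, week-1 value, week-1 value-by-week and gender (the randomization factor).
- **(b)** Weeks 1, 4 and 8 as responses, with one common week-1 mean for both arms (no group effect at week 1), and gender-by-week.

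Route (b) keeps participants who have only a week-1 value and so fits the promise of "accounting for the correlation with the repeated measurements of each participant, and using all available data". Route (a) drops them: 6 of 60 if 10% leave after week 1.

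With either route:
- Use an unstructured covariance, test the group effect over both weeks jointly, and report the week-8 contrast.
- State that the week-1 score is not to be added merely as a main effect while week 1 remains an unconstrained response.
- Fix any further covariates in advance instead of choosing them by comparing the arms at baseline.
- Keep the change-from-week-1 model, with an unstructured covariance, as a sensitivity analysis, because baseline is taken after allocation at an arm-dependent place. The two results may differ.
- Do not apply either route to HRV or salivary markers unless their week-1 value is confirmed to precede session 1. Outcome Assessment describes HRV recording during and after sessions.

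The cost is SAP wording, analysis syntax and one sensitivity analysis. No new data are needed.
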